# Acute Effects After Dosing: Other assessments with binary response (normal/abnormal; present/absent)

On each dosing day, the shifts from predose assessment on that day to postdose (i.e., from predose to 3, 6 and 24 hours postdose) will be determined. For each test and post dosing time point, the number and proportion of subjects who moved from 'normal' to 'abnormal' will be presented, for sensations the number and proportion who move from 'present' to 'absent' will be presented.

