# 6.1.3. Neurological Examinations

Neurological examinations include assessment of mental status, level of consciousness, cranial nerves, reflexes, motor system, coordination/cerebellar function and sensation – temperature and vibration. These are to be assessed at Screening, predose and at 3, 6, and 24 hours postdose on dosing Days 1, 15, predose and at 1 and 3 hours postdose on Days 29, 64, 135, 183, and 279; and at Day 302/ET.

The results collected for the majority of the tests are classified as 'normal' or 'abnormal', however the assessment of sensations is reported as 'present' or 'absent' and the assessment of reflexes is captured on an ordinal scale. For each test it is recorded if secondary to SMA.

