#### **3.2.** Study Treatment

All participants will receive a single bolus dose of 50 mg of nusinersen administered intrathecally on Day 1 of this study (which should be administered 4 months  $\pm$  14 days after their most recent maintenance dose of 12 mg), followed by 2 maintenance doses of 28 mg of nusinersen on Days 121 and 241.

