# 5.7.3.2. Neurological Examination in patients 2 years or older

Neurological examinations include assessment of mental status, level of consciousness, cranial nerves, reflexes, motor system, coordination/cerebellar function and sensation – temperature and vibration. These are to be assessed at Screening, predose and at 3, 6, and 24 hours postdose on Day 1, predose and at 1, 3 hours on Days 121 and 241, and on Day 302/ET.

The results collected for the majority of the tests are classified as 'normal' or 'abnormal', however the assessment of sensations is reported as 'present' or 'absent' and the assessment of reflexes is captured on an ordinal scale. For each test it is recorded if secondary to SMA.

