# Acute Effects After Dosing: Reflex assessments

On each dosing day, each predose reflex will be compared with all the post dosing assessments with 24 hours to see if the subject has changed (gained or lost) or maintained, reflexes. For this comparison the predose reflex status will be categorized into two categories: 0 and  $\geq 1$ . For each reflex, visit, predose category the number and proportion of subjects who change or maintained will be presented.

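### In Part C (age 2 or older) and Part B later-onset, the hour list for the acute non-reflex neurological shifts does not match the exam schedule, and read literally it omits the 1-hour exam on most dosing days

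*SAP*

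**What the plan says.** **Part C SAP, section 5.7.3.2 (participants 2 years or older).** Exams are scheduled "predose and at 3, 6, and 24 hours postdose on Day 1, predose and at 1, 3 hours on Days 121 and 241", and again at Day 302 or early termination. The acute rule for the binary tests then reads "On each dosing day, the shifts from predose assessment on that day to postdose (i.e., from predose to 3, 6 and 24 hours postdose"), and the output is described as "For each test and post dosing time point, the number and proportion of subjects who moved from 'normal' to 'abnormal' will be presented". For sensation the corresponding shift is from present to absent.

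**Part B later-onset SAP, section 6.1.3.** Days 1 and 15 have exams at 3, 6 and 24 hours after dosing. The remaining procedure days have exams "predose and at 1 and 3 hours postdose on Days 29, 64, 135, 183, and 279". The acute rule for the binary tests carries the same 3, 6 and 24 hour list ("predose to 3, 6 and 24 hours postdose) will be determined") and also applies to each dosing day.

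**Reflexes, both SAPs.** The acute rule is open: "each predose reflex will be compared with all the post dosing assessments" over 24 hours. It names no hours.

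**Chronic tables for the binary tests, both SAPs.** These compare the Day 1 pre-dose value with later pre-dose values and with Day 302 or early termination.

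**The concern.** The schedule and the analysis rule stand in the same section of each SAP and do not agree. On the later dosing days the rule names two times with no scheduled exam (6 and 24 hours) and does not name the 1-hour exam, which is the earliest after the intrathecal procedure. A programmer who follows the list would not tabulate it. A participant normal before dosing, abnormal at 1 hour and normal again at 3 hours would not be counted as a shift. The chronic tables would not count that participant either, because within the dosing days they use pre-dose values only.

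Change from baseline in neurological examination outcomes is a primary endpoint of Part C (section 2.1) and a secondary safety endpoint of Part B later-onset (section 2). The acute table supports that endpoint. The groups are small, about 40 participants in Part C and 24 in Part B later-onset, so a few uncounted transient shifts could visibly change a reported proportion.

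**Working it through.** The plan states no figure to reproduce. The check is a count of scheduled post-dose exams against the hours named in the acute rule.

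**Inputs**
- Part C dosing days: Day 1, "followed by 2 maintenance doses of 28 mg of nusinersen on Days 121 and 241" (section 3.2), so three days.
- Part C exam times: section 5.7.3.2.
- Part B later-onset procedure days: 1, 15, 29, 64, 135, 183 and 279 (section 2.1), so seven days. Section 6.1.3 treats all seven as dosing days, including those on which an arm receives a sham procedure.
- Part B later-onset exam times: section 6.1.3.
- Hours named in both acute rules: 3, 6 and 24.

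**Formulas**
- Scheduled exams = sum over days of post-dose exam times.
- Omitted = scheduled exams at an hour not in the list.
- Empty cells = (days × 3 listed hours) − scheduled exams that are in the list.

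| | Part C, age 2 or older | Part B later-onset |
|---|---|---|
| Days with exams at 3, 6, 24 h | 1 | 2 |
| Days with exams at 1, 3 h | 2 | 5 |
| Scheduled post-dose exams | 3 + 2×2 = 7 | 2×3 + 5×2 = 16 |
| Covered by the list | 3 + 2×1 = 5 | 6 + 5×1 = 11 |
| Omitted (all at 1 h) | 7 − 5 = 2 (2/7 = 29%) | 16 − 11 = 5 (5/16 = 31%) |
| Day-by-hour cells implied | 3×3 = 9 | 7×3 = 21 |
| Cells with no scheduled exam | 9 − 5 = 4 | 21 − 11 = 10 |

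**Part B later-onset by arm.** In the 50/28 mg arm the five affected days are the two 28 mg doses (Days 135 and 279) and three sham days (29, 64 and 183). Counting active doses only (Days 1, 15, 135, 279), the omission is 2 of 3 + 3 + 2 + 2 = 10 exams, or 20%. In the 12 mg arm the affected days are four active doses (29, 64, 183, 279) and one sham day (135). Counting active doses only, the omission is 4 of 3 + 3 + 4×2 = 14 exams, or 29%.

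**Comparison with other rules**
- Part B infantile-onset SAP (section 7.1.4): exams are at 3, 6 and 24 hours on every dosing day and the acute rule names the same hours, so list and schedule agree.
- Vital signs in Part C (section 5.7.5) and Part B later-onset (section 6.1.5) also have a reduced schedule on later days. Their acute rule gives examples and leaves the list open, so it adapts.
- Of the acute rules in these two SAPs, only the one for the non-reflex binary tests combines a closed list with a schedule that differs from it. No reason is given.

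**The case against.** **The 1-hour exam may not be dropped at all.** The sentence that defines the output asks for results at each post-dose time point and names no hours. Read with the schedule, that takes in 1 hour. The list also fits the infantile-onset SAP exactly, so it looks more like carried-over text than a decision to discard an exam. This stands in part. A reader might infer that the exam is certain to be excluded, and the text does not establish that. But the list is introduced as a definition and is closed, so two programmers could build different tables from it.

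**Other reporting could show the event.** The Part C SAP (section 5.7) has new or worsened neurological findings reported as adverse events where appropriate, and section 5.7.1 tabulates adverse events within 24 and 72 hours of dosing. The Part B later-onset SAP has the same two adverse event tables (section 6) and plans figures of subjects' neurological exams (section 6.1.3). This stands: the event need not vanish from the report. These routes do not supply the shift proportion that the table is meant to give.

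**The affected signal is narrow.** The 3-hour exam is tabulated on every affected day and reflexes at 1 hour are used, so only a binary abnormality resolved by 3 hours is missed. The acute table compares with the same day's pre-dose value, so it supports the change-from-baseline endpoint and is not its direct summary. Both points stand. The percentages above count scheduled exams, not lost events.

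**Reflexes and binary tests may be summarised differently.** True. The differing rules are not in themselves a contradiction. The fault lies in the binary rule against its own schedule.

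**Conclusion.** The mismatch is real and limited to two places: the acute rule for non-reflex binary tests in the Part C SAP (participants 2 years or older) and in the Part B later-onset SAP. On the literal reading it omits 2 of 7 and 5 of 16 scheduled post-dose exams, all at 1 hour, and calls for 4 of 9 and 10 of 21 day-by-hour results that have no scheduled exam. A binary abnormality seen at 1 hour and gone by 3 hours would then be in no specified shift table.

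The counts assume that the section text gives the full exam schedule and that sham days count as dosing days, as section 6.1.3 treats them.

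A reader might go further and conclude that the earliest exam is lost for every 28 mg maintenance dose in the study. The documents do not support that. Part B infantile-onset participants receive 28 mg on Days 135 and 279 under a schedule that the list matches. Part A plots and lists all neurological items for each subject. Part C participants under 2 years have their results listed only (section 5.7.3.1). These are descriptive safety tables, and no hypothesis test or efficacy result depends on them.

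**What to change.** In the acute rule for binary tests in Part C section 5.7.3.2 and in Part B later-onset section 6.1.3, replace the fixed hours with: from predose to each scheduled postdose assessment on that day. The table then follows the schedule stated earlier in each section and no longer has cells that cannot be filled. A further row for any shift within 24 hours would parallel the reflex rule but is optional.

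The cost is one phrase in each SAP and a 1-hour column in an existing table. No exam is added and no clinical procedure changes.

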# Chronic effects: Other assessments with binary response (normal/abnormal; present/absent)

For each test the shift from baseline to (the predose value on Day 1) to the predose value on later dosing days and to Day 1, 121, 241 and on Day 302/ET will be determined, the number and proportion of subjects who moved from 'normal' to 'abnormal' will be presented, for sensations the number and proportion who move from 'present' to 'absent' will be presented.

# 5.7.4. ECG

ECGs are to be recorded at Days 1, 121, 241, and 302/ET, predose (Day 1) and post dosing (Days 1, 121, 241) at various time points on dosing days and end predose at 302/ET. The ECGs are assessed at a central reading laboratory and the results provided as external vendor data. On the eCRF the investigator interpretation is collected as normal, abnormal and abnormal AE and the investigator determination will be used in analyses.

Product: Nusinersen	Statistical Analysis Plan
Study: 232SM203	Version: 1.0 Final

The ECG test includes heart rate, QT interval, QTcF interval and RR interval. Summary statistics for actual values and change from baseline in each ECG parameter will be presented by study group and visit.

ECGs will be analyzed using two approaches.

# Qualitative analysis

The determination of whether an ECG is abnormal not AE, abnormal AE made by the Investigator will be used for this qualitative analysis.

The number and percentage of subjects with shifts from normal to each of the categorical values denoting an abnormal scan (abnormal not AE, abnormal AE) will be summarized by study group. All post baseline data will be used to identify abnormalities, regardless of whether a scheduled or unscheduled visit.

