#### **Study Primary Endpoints (Part C)**

- Incidence of adverse events (AEs), including serious adverse events (SAEs)
- Shifts from baseline in clinical laboratory parameters, electrocardiograms (ECGs), and vital signs
- Change in growth parameters
- Shifts from baseline in coagulation parameters (activated partial thromboplastin time [aPTT], prothrombin time [PT], and international normalized ratio [INR])
- Change in urine total protein
- Change from baseline in neurological examination outcomes
- The proportion of participants with a post-baseline platelet count below the lower limit of normal on at least 2 consecutive measurements
- The proportion of participants with a post-baseline QT interval using Fridericia's formula (QTcF) of > 500 msec and an increase from baseline to any post-baseline timepoint in QTcF of > 60 msec

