#### 5. Statistics Methods for Planned Analyses

#### 5.1. General Principles

Descriptive summary statistics will be presented for all primary, secondary **secondary** endpoints collected. Unless otherwise specified, for continuous endpoints, the summary statistics will generally include number of participants with data, mean, standard deviation, median, 25th percentile, 75th percentile, minimum and maximum. For categorical endpoints, the summary statistics will generally include number of participants with data, and the percentage of those with data in each category.

All summaries and listings will be presented by study groups unless otherwise specified. Visits in listings will be displayed as per CRF data collection rather than analysis visits. The statistical software, SAS®(Version 9.4) will be used for all summaries and statistical analyses.

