For each hematology, blood chemistry, coagulation and CSF parameter, the number and percentage of subjects experiencing postdose shifts to 'low' or 'high' will be summarized. In each summary, the denominator for the percentage is the number of subjects at risk for the shift. The number at risk for the shift to low is the number of subjects whose baseline value was not low and who had at least one post baseline value. The number at risk for the shift to high is the number of subjects whose baseline value was not low and who had at least one post baseline value. The number at risk for the shift to high is the number of subjects whose baseline value was not low and who had at least one post baseline value. The number at risk for the shift to high is the number of subjects whose baseline value was not high and who had at least one-post baseline value. Subjects will be counted only once for each parameter and each shift regardless of how many postdosing assessments had that type of shift. All post baseline data will be used in the shift tables, regardless of whether a scheduled or unscheduled visit.

Also, for each parameter, the incidence of shift to low will be summarized using the minimum post baseline values. Shift to low includes subjects with a normal, high, or unknown baseline value and at least one post baseline value of the given test. Similarly, the incidence of shift to high will be summarized using the maximum post baseline values. Shift to high includes subjects with a low, normal, or unknown baseline value and at least one post baseline value.

To evaluate potential serious hepatotoxicity subjects with a post baseline AST and/or ALT value  $\geq$ 3 times the upper limit of normal (ULN) and a post baseline bilirubin value >2 times ULN at any time, not necessarily concurrent, will be listed with their values. In addition, a plot will be

Product: Nusinersen	Statistical Analysis Plan
Study: 232SM203	Version: 1.0 Final

presented with each subject's maximum post baseline AST or ALT value relative to the ULN against the subject's maximum post baseline bilirubin value relative to the ULN; values do not have to be concurrent. All post baseline data will be used to identify abnormalities, regardless of whether a scheduled or unscheduled visit.

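### The qualitative ECG shift table has no place for worsening from an abnormal or unknown baseline, and the ECG and binary neurological shift percentages have no stated denominator

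*SAP*

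**What the plan says.** Part C lists among its primary endpoints (section 2.1) "Shifts from baseline in clinical laboratory parameters, electrocardiograms (ECGs), and vital signs".

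For the ECG (section 5.7.4), "On the eCRF the investigator interpretation is collected as normal, abnormal and abnormal AE and the investigator determination will be used in analyses". The qualitative analysis then gives the number and percentage of subjects with "shifts from normal to each of the categorical values denoting an abnormal scan (abnormal not AE, abnormal AE". No other starting category is mentioned and no denominator is given. The qualitative analyses in 7.1.5 of the Part B infantile-onset SAP and 6.1.4 of the Part B later-onset SAP have the same restriction.

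For the binary neurological tests (section 5.7.3.2, acute and chronic effects), the number and "proportion of subjects who moved from 'normal' to 'abnormal' will be presented", and for sensations the move from present to absent. Again no denominator is given.

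The general default (section 5.1) for categorical endpoints is the "number of participants with data, and the percentage of those with data in each category". It is qualified as what summaries will generally include unless otherwise specified.

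For laboratory shifts (section 5.7.2) the plan does specify otherwise: "In each summary, the denominator for the percentage is the number of subjects at risk for the shift". It also keeps participants with an unknown baseline in the incidence of shift to low or high.

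**The concern.** Two features of these tables sit badly with an endpoint defined as shift from baseline.

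First, the ECG reading separates abnormalities the investigator regards as adverse events from those that are not. A move across that line after dosing is a change a safety reader would want to see. The table starts only from normal, so it has no cell for it.

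Second, a shift percentage is hard to read without knowing who could have shifted. A participant already abnormal at the reference examination cannot move from normal to abnormal. If such participants sit in the denominator, the percentage falls as baseline abnormality rises, whatever happens on treatment. This is a practical issue for the neurological examination, because the plan records for each test whether the finding is secondary to SMA and so expects disease-related abnormality.

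At stake is how completely and how clearly a descriptive safety endpoint is reported: primary in Part C, secondary safety in Part B.

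**Working it through.** The SAP gives no rate, sample size or power figure for these tables, so there is nothing of its own to reproduce. The check is a comparison of rules followed by simple arithmetic.

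**Which ECG moves are counted in the 5.7.4 table**

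| Baseline reading | Post-baseline reading | Counted? |
|---|---|---|
| normal | abnormal not AE | yes |
| normal | abnormal AE | yes |
| abnormal not AE | abnormal AE | no |
| unknown | abnormal not AE or abnormal AE | no |

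The other ECG summaries in 5.7.4 are heart rate, QT, QTcF and RR by visit, and QTcF outliers. They are not restricted to normal baselines, but they do not summarise the investigator's reading.

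**Does the same gap reach the neurological tests?** No. Reflexes are tabulated as changed (gained or lost) or maintained, within each predose category. The remaining items have two levels, so there is no worsening within 'abnormal' to lose. Only the denominator question applies to them.

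**Effect of the denominator, if the section 5.1 default is used**

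Inputs: N = 40 (Part C enrolment, stated in the introductions of the Part B SAPs); f = share abnormal at baseline, which no SAP gives, so an assumed range; p = rate of moving from normal among those normal at baseline, assumed 10%.

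Printed percentage = p × (1 − f). At-risk percentage = p.

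| f (assumed) | Normal at baseline | Printed over those with data | Printed over those at risk |
|---|---|---|---|
| 0% | 40 | 10.0% | 10% |
| 10% | 36 | 9.0% | 10% |
| 25% | 30 | 7.5% | 10% |
| 50% | 20 | 5.0% | 10% |
| 75% | 10 | 2.5% | 10% |

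The understatement factor is 1 − f, and it vanishes when everyone is normal at baseline.

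The factor also differs between columns with different baseline status. Display 'a' in section 3.3 sets infantile-onset beside later-onset groups. If one column had f = 10% and another f = 50% (assumed), the same 10% rate would print as 9.0% and 5.0%.

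For a single new neurological abnormality among 40, the printed figure is 1/40 = 2.5%. The at-risk figure is 1/[40 × (1 − f)]: 1/20 = 5% at f = 50%, 1/12 = 8.3% at f = 70%, and 1/4 = 25% at f = 90% (all assumed).

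**Effect of the missing ECG cell (illustration)**

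Assume 30 participants normal and 10 'abnormal not AE' at baseline, with 2 new 'abnormal AE' readings from each group. The table as written counts 2: 2/40 = 5.0% over those with data, or 2/30 = 6.7% over those normal at baseline. Counting everyone not already 'abnormal AE' at baseline gives 4/40 = 10.0%.

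**The case against.** The strongest reply is that the information is not lost. An ECG rated 'abnormal AE' is by its label an adverse event. If new or worsened after the first study dose, it enters the treatment-emergent tables in 5.7.1 whatever the baseline ECG, and the ECG listings carry both the central and the eCRF reading. That stands, so a reader who infers that such worsening is never reported would be wrong. What remains is that the adverse event tables do not show it as a change from the baseline ECG, which is how the endpoint is defined.

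The second reply is that the ECG and neurological sections do not say the percentages run over all participants with data. That too stands. The default in 5.1 is hedged, and a percentage of subjects shifting from normal could be read as a percentage of those who began normal. The supportable statement is that the denominator is unspecified and would fall to the default. Two programmers could reasonably produce different figures.

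Third, the counts are shown beside the percentages and do not depend on the denominator, and no test or decision rule uses these tables. That is correct and limits the importance.

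Fourth, a predose Day 1 ECG is scheduled, so unknown baselines may be few. That is fair; including the category costs one row.

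**Conclusion.** The point holds within limits. In all three SAPs the qualitative ECG table counts only shifts from normal, so worsening from 'abnormal not AE' to 'abnormal AE', or an abnormal reading after an unknown baseline, is not counted there. The denominator for the ECG and binary neurological shifts is unstated, while the laboratory shifts in the same plan use participants at risk. If the general default applies, the shift percentage is understated by a factor equal to the share normal at baseline.

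That size cannot be derived from the documents; every baseline-abnormal share used here is an assumption, and the understatement could be nil.

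A reader might infer two stronger things. One is that the neurological tables also miss worsening; they do not, because reflexes are split by starting status and the other items are binary. The other is that every participant with an abnormal baseline ECG is lost to safety reporting. In fact the table misses such a participant only on a later move to 'abnormal AE', and the adverse event tables and listings can still show that event.

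The consequence is confined to descriptive safety tables. The change is still worth making, because the affected endpoint is primary in Part C and the data are already collected.

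**What to change.** In 5.7.4 of the Part C SAP, 7.1.5 of the Part B infantile-onset SAP and 6.1.4 of the Part B later-onset SAP, tabulate baseline category (normal, abnormal not AE, abnormal AE, unknown) against worst post-baseline category, and count 'abnormal not AE' to 'abnormal AE' as a shift.

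State the denominator for the ECG shifts and for the binary neurological shifts in 5.7.3.2 as participants at risk, following the principle in 5.7.2. For the neurological tests this means those normal (for sensations, present) at the reference examination with a later value. The binary neurological wording in 6.1.3 of the Part B later-onset SAP is the same and should be aligned.

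Cost: a few sentences and a slightly larger descriptive table. No new data are needed.
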